Secondary Objectives	(ii) evaluate the effects of HD-tDCS on functional connectivity using functional Magnetic Resonance Imaging (fMRI), and (iii) elucidate its effects on spontaneous neuronal oscillatory patterns using Magnetoencephalography (MEG).
Endpoints	
 • Primary outcome measurements: Language performance changes as assessed at baseline and after tDCS stimulation procedures (time frame: 2 weeks). • Secondary outcome measurements: (ii) Changes in brain functional connectivity as assessed at baseline and after tDCS stimulation (time frame: 2 weeks) (iii) Changes in abnormal patterns of neuronal frequencies and synchronizations as assessed at baseline and after tDCS stimulation procedures (time frame: 2 weeks).

Study Design	
This clinical utility study is a randomized, double-blind, sham-controlled trial in which stimulation or sham will be administered to 20 subjects over the age of 45 years, with the order of treatments counterbalanced in a within-subject crossover design. Stimulation and sham sessions last 20 minutes and occur for 10 days over a 2-week period.
 
The study consists of Pre-screening (Visit –1), Baseline (Visit 1), a 2-week Treatment Period (Visits 1-10), a 16-week Washout Period, an Interim Assessment (Visit 11), a second 2-week Treatment Period (Visits 12-21), and a Final Assessment (Visit 22).

Study Agent/ Intervention Description	tDCS and sham stimulation sessions lasting 20 minutes at a current intensity of up to 2mA in the targeted cortical tissue
Number of Subjects	20
Subject Participation Duration	28 weeks: 2 weeks of tDCS/sham, followed by a 16-week washout, followed by 2 weeks of tDCS/sham, followed by an 8-week final assessment.
Duration of Follow up	None
Estimated Time to Complete Enrollment	18 months
Statistical Methodology	The collection of pilot data from this study will provide initial estimates of the variability and the effect sizes. This information will then be used for the more formal calculations of power and sample size necessary to conduct a pivotal trial. All future statistical testing will use repeated measures ANOVA once a large enough sample is reached.
Safety Assessments	Data safety monitoring board meetings will be scheduled to monitor progression of the study and review drug adverse events

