1.2. Objectives

To determine whether active HD-tDCS targeting the dominant posterior TPC can improve language performance, increase language network functional connectivity, and improve abnormal patterns of resting state neuronal frequencies and synchronizations.

Specific Aim 1. Determine changes in language performance after 10 HD-tDCS stimulation sessions (QD) lasting 20 minutes at a current intensity of up to 2mA in the left TPC in a randomized, double-blind, sham-controlled, within-subject cross-over study with 20 lvPPA subjects ages 45 years and greater.

Specific Aim 2. Determine the effects of the conditions described in Specific Aim 1 on the resting state Language network-level changes in left TPC functional connectivity between the conditions described in Specific Aim 1.

Specific Aim 3. Determine the effects of the conditions described in Specific Aim 1 on the neuronal frequency distribution and connectivity measures associated with the left TPC as assessed by MEG.

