1.3. Outcome Measurements

The following outcome measurements will be used to test our proposed hypothesis:

- **Primary outcome measures:** Language performance as assessed at baseline and post-stimulation procedure (time frame: 2 weeks)
- **Secondary outcome measures:** Language network resting state changes after stimulation procedure (time frame: 2 weeks)
- **Tertiary outcome measures:** Resting-state neuronal frequencies and synchronizations changes after stimulation procedure (time frame: 2 weeks)

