The rsMEG datasets will be obtained at baseline (before sham/active tDCS administration) and on the last day of each 2-week treatment period. For data analysis we will use the well established Epilepsy Connectome Project (ECP) MEG methods, currently used at MCW. A scalp digitization will be generated during each session of the MEG procedure that includes anatomical landmarks and localizer coils. The MEG data will be co-registered to the MRI using a minimization of the distance from the digitized headshape to the MRI derived scalp surface. The localizer coils will provide the position of the patients head relative to the MEG sensors. Sensor level activity will be projected to the cortical surface using minimum norm based spatial filters with anatomical priors. The cortical surface will be downsampled to approximately 8000 vertices; the orientation and location will act as priors on solving the transformation from sensor space to source space, known as the inverse solution. Data from the cortical surface will be spatially averaged over the anatomical parcellations. These parcellated timeseries will be used to calculate band-limited connectivity measures. Targeted exploration of connectivity driven by current understanding of the pathophysiology of lvPPA will also be pursued.

Connectivity between all ROI-pairs will be calculated in the theta (4-8 Hz), alpha (8-12 Hz), beta (13-30 Hz), and low-gamma (30-55 Hz) frequency bands using three different metrics: coherence (COH), phase lag index (PLI), and debiased weighted phase lag index (d-wPLI). Mean connection strengths within 3 intra-hemispheric language-specific ROI-groups, and those between all intra-hemispheric ROIs will be computed. We will also compute mean connection strengths between language ROI-groups and all remaining brain ROIs, and those between each hemispheric ROI and all other brain ROIs.

The same multiple linear regression models used for the analysis of rsfMRI data will be used for the analysis of rsMEG data (for simplicity, regression equations are not shown). See above for details.

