6.7. Expected Results, Deliverable, and Problems

Through this study, we expect to realize two goals: **Scientifically**, we will demonstrate that active HD-tDCS can increase language-network functional connectivity and improve abnormal patterns of resting state neuronal frequencies and synchronizations. **Clinically**, we expect that the changes in network activity after the 2-week stimulation period will lead to language improvement. This study can provide conceptual proof for a rehabilitation intervention. In addition, this study will provide information and address the power of adequate enrollment, protocol adherence, subject retention, and safety for future pilot and pivotal trials.

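### Aim 3 promises an effect on MEG frequencies as well as synchronizations, but section 6.6 derives only connectivity, so the frequency component has no measure

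*Protocol*

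**What the plan says.** The promise has two parts wherever it appears in the protocol.

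- Section 1.2, Specific Aim 3: the effect on "neuronal frequency distribution and connectivity measures associated with the left TPC as assessed by MEG".
- Protocol Summary, Endpoints (MEG listed as secondary): "Changes in abnormal patterns of neuronal frequencies and synchronizations as assessed at baseline and after tDCS stimulation procedures".
- Section 1.3 (MEG listed as tertiary): "Resting-state neuronal frequencies and synchronizations changes after stimulation procedure".
- Section 6.7, expected results: that active stimulation can "improve abnormal patterns of resting state neuronal frequencies and synchronizations".

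The analysis in section 6.6 has one part. After source projection and averaging over parcels, "These parcellated timeseries will be used to calculate band-limited connectivity measures". It continues: "Connectivity between all ROI-pairs will be calculated in the theta (4-8 Hz), alpha (8-12 Hz), beta (13-30 Hz), and low-gamma (30-55 Hz) frequency bands". The metrics are coherence (COH), phase lag index (PLI) and debiased weighted phase lag index (d-wPLI), summarized as mean connection strengths within and between groups of regions. The additional targeted exploration is also of connectivity. The MEG data then go into the regression used for resting-state fMRI. Its covariates (section 6.4) are age, education, gender and gray matter volume, all declared time-invariant.

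The SAP covers item-level language scores within participants. It mentions no MEG measure, and it says that the sample was too small for group-level testing.

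**The concern.** How activity at the left posterior temporo-parietal cortex (TPC) is distributed over frequency is a property of the power spectrum of that region. Coherence, PLI and d-wPLI describe how two regions relate to each other within a band. The second does not give the first. Followed exactly, the plan would produce many connectivity results and nothing that speaks to the frequency part of Aim 3.

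The omission also affects how the connectivity results can be read. Estimated coupling depends on signal-to-noise. If stimulation changes band power, which the frequency hypothesis itself allows, apparent synchronization can change with no change in coupling. The plan reports no band power that would let a reader see this.

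**Working it through.** The plan states no figure for the MEG endpoint (no sample size, power, alpha or effect size), so there is none to reproduce.

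**1. Count of derived MEG quantities (section 6.6).**
- Connectivity: 4 bands × 3 metrics = 12 per regional summary.
- Spectral (band power, relative power, mean or peak frequency): 0, in section 6.6 or anywhere else in the protocol or SAP.

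**2. Effect of band power on coherence.** Assumptions, none of them from the documents: two regions with equal signal-to-noise S, noise independent between regions, true coupling fixed. Independent noise adds nothing to the cross-spectrum but inflates each auto-spectrum by (1+S)/S. Hence

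- measured coherence = true coherence × S/(1+S)
- measured squared coherence = true squared coherence × [S/(1+S)]²

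For a 20% rise in power:

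| S before → after | S/(1+S) | Change | [S/(1+S)]² | Change |
|---|---|---|---|---|
| 1 → 1.2 | 0.500 → 0.5455 | +9% | 0.2500 → 0.2975 | +19% |
| 5 → 6 | 0.833 → 0.857 | +3% | 0.6944 → 0.7347 | +6% |

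Section 6.6 says only coherence and does not state the scale, so both are shown.

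**3. All three metrics by simulation.** Assumed settings: source coherence 0.6, phase lag π/4, 360 epochs, independent noise of variance 1. Results are averages over repeated runs.

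| Condition | COH | PLI | d-wPLI |
|---|---|---|---|
| Power/noise 0.5 | 0.20 | 0.15 | 0.08 |
| Power/noise 1 | 0.30 | 0.21 | 0.17 |
| Power/noise 2 | 0.40 | 0.30 | 0.30 |
| Power/noise 4 | 0.48 | 0.36 | 0.40 |
| No noise, power 0.5, 1 or 2 | 0.60 | 0.47 | 0.59 |

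The simulated coherences agree with 0.6 × P/(P+1): 0.20, 0.30, 0.40 and 0.48.

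In a separate run with no true coupling, a third source leaked into both regions at zero lag. Raising its power from 1 to 4 lifted COH from 0.20 to 0.50. PLI stayed near 0.04 and d-wPLI near 0.

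So signal-to-noise moves all three metrics, zero-lag leakage moves coherence only, and amplitude scaling without noise moves none.

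**4. Could the planned model absorb it?** No. Every covariate is time-invariant, so none can account for a change within a participant from before to after treatment.

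**The case against.** The best case on the other side has five parts.

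- *The Aim 3 rationale is about connectivity.* The MEG studies cited in section 3.1 concern connectivity, and band-resolved coupling fits them. The fault may be loose endpoint wording. This stands as a possibility, so the fix offers a wording route. It does not remove the mismatch, because Aim 3 lists frequency distribution separately from connectivity.
- *The external pipeline may produce spectra.* Section 6.6 adopts an established MEG pipeline whose outputs the documents do not list. It may compute power, but no such outcome is named.
- *PLI and d-wPLI protect against artefact.* They do against zero-lag leakage, but not against a change in signal-to-noise.
- *The randomized sham crossover balances drift.* It should, on average, for signal-to-noise drift unrelated to treatment. It does not separate a power change caused by stimulation from a coupling change. The recordings are kept, so power could be computed later; the plan simply does not report it.
- *The endpoint is minor.* It is secondary in the summary and tertiary in section 1.3, in a pilot. This stands and limits the consequence.

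A reader might also infer stronger conclusions that the documents do not support. One is that any observed gain in synchronization would be a power artefact; the working shows only that it could be. Another is that a connectivity change should count as synchronization only after adjustment for power. Power measured after stimulation may itself be changed by stimulation, so conditioning on it can remove part of a real effect or add bias, and the sample is small. A third is that a band below 4 Hz is required. The documents never define the abnormal patterns as slowing and mention nothing below 4 Hz.

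**Conclusion.** The point holds as a gap between endpoint and analysis. One of the two named components of the MEG endpoint has no derived measure (0 spectral quantities against 12 connectivity quantities per regional summary), and the SAP does not supply one. This rests on the text alone.

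The possible misreading of connectivity is a secondary matter. Under the stated model more power relative to noise raises all three metrics, but the size depends on assumption: about 3% to 9% for coherence and 6% to 19% for squared coherence, for a 20% power rise at signal-to-noise 5 and 1. The 19% figure is specific to squared coherence at signal-to-noise 1 and should not be quoted alone.

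The primary language outcome is unaffected. What is at stake is an unanswerable part of Aim 3 and an ambiguous reading of mechanism.

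**What to change.** In section 6.6, compute the power spectrum of the left TPC parcels from the same resting recordings. Name one summary as the frequency-distribution measure of Aim 3, for example relative power across the four stated bands or spectral mean frequency. Report band power descriptively beside each connectivity result, per participant, given the SAP's limit on group-level analysis. Label the measure as added after the protocol. Do not make adjustment for power a condition for interpreting connectivity. A delta band is optional.

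If the sponsor does not intend to study frequencies, remove that component from the Protocol Summary, sections 1.2 and 1.3, and the expected results in section 6.7, so that they match section 6.6.

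Cost: a few lines of text, minor analysis time on time series the plan already produces, and one more exploratory measure. No new recording is needed.

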6.7. Expected Results, Deliverable, and Problems

Through this study, we expect to realize two goals: **Scientifically**, we will demonstrate that active HD-tDCS can increase language-network functional connectivity and improve abnormal patterns of resting state neuronal frequencies and synchronizations. **Clinically**, we expect that the changes in network activity after the 2-week stimulation period will lead to language improvement. This study can provide conceptual proof for a rehabilitation intervention. In addition, this study will provide information and address the power of adequate enrollment, protocol adherence, subject retention, and safety for future pilot and pivotal trials.

6.8. Data Sharing

Subjects will provide written informed consent via an addendum consent form, noting their permission for the study team to share all data collected throughout their participation in the study with UW-Madison collaborator

[name] in the Department of Communication Sciences and Disorders and her team. [name] and her team will analyze the study data and provide statistical support to the MCW study team.

The following data will be sent to [name] in a secure and protected manner:

- Study ID number
- Dates of visits and consent
- Demographic information, such as age, year of birth, sex, handedness, race, ethnicity, educational history, and childbearing potential
- Medical history, such as medical/neurological diagnoses and medications
- Randomization information
- Adverse events
- TMS Neuronavigation data
- Performance on cognitive and language tests
- Voice recordings and speech samples
- Images from MRI scan
- Recordings from MEG scan

Once data analysis and statistical support are complete, [name] send results back to the study team, where they will be stored for the duration of the study.

The data we provide will not contain any information that can directly identify subjects.

7. DATA SAFETY MONITORING PLAN

An appointed DSMB will discuss the ethical conduct of the trial, review event definitions and the subject ICF form, and further develop plans for monitoring the data and safety of the trial. The DSMB will meet at least annually to review the course of the trial. The DSMB agrees to communicate with institutional review board (IRB)/human subject committees to provide reassurances, as appropriate. There will be three DSMB members with the following areas of expertise:

- Neural mechanism underlining language and memory disorders.
- Neuroimaging
- Psychology of Language and Memory Loss.

7.1. Safety Plan

The safety issues in this study are related to use of HD-tDCS and acquisition of fMRI and MEG data. This study uses a well-known HD-tDCS montage at a safe dose of current. Previous studies on the safety and tolerability of tDCS have shown that a 2-mA current applied for 20 minutes is associated with no serious AEs (Brunoni et al., 2011). The AEs most often associated with HD-tDCS are not associated with long-term, deleterious effects, and instead are typically mild and transient in nature. The most commonly reported AEs are itching, tingling, mild headache, mild fatigue and localized burning sensation at the site of stimulation. (Brunoni et al., 2011). We will assess AEs using a customized questionnaire (Attachment 1). The questionnaire will be performed immediately after each tDCS session and during the phone follow-up calls scheduled between treatment periods.

7.2. MRI Safety

The MRI scanner device is a U.S. Food and Drug Administration (FDA)-cleared device for safe and noninvasive imaging of the interior of the human body. The GE MR750 MRI uses a 32-channel receive-only head coil, which is an investigational device. See below for further information on the 32-channel receive-only head coil. The proposed MRI scans are NOT for a use of substantial importance in diagnosing, curing, mitigating, or treating disease or otherwise preventing impairment of human health, and they do not present a potential for serious risk to the health, safety, or welfare of a subject. The scanner also restricts the software from exceeding FDA safety levels. The scanner monitors the SAR for research scans just as it does for all other scans. Thus, the scanner

with the software fully engaged operates, from a technical design and functional standpoint, as a **nonsignificant risk** device in accordance with 21 CFR 812. By staying below these limits, the operating conditions of the MRI device are generally deemed, in and of themselves, to make the MRI device a nonsignificant risk device.

The Nova Medical 32-channel head coil (model number NMSC075-32-3GE-MR750) is an investigational device that is not approved by FDA for clinical use. This coil device includes multiple features for safe operation involving human studies. The 32-channel coil is designed and constructed as a receive-only detector of RF signals that are emitted by the brain following the RF excitation generated by the GE Healthcare MRI scanner, which is FDA approved. During the RF excitation by the scanner, the coil device is decoupled (made inactive) through redundant circuitry; thus, the coil device never transmits RF to the subject and, therefore, it has no impact on subject risk or safety.

More specifically, the coil design and construction include the following safety features: **1)** High-voltage breakdown (>2 kV) UL-94V0 flame retardant housing. **2)** Rugged construction to ensure safe operation in case of rough handling. **3)** Active detuning circuitry providing greater than 35 db isolation per element. **4)** High power passive detuning circuits in case primary detuning circuitry fails. **5)** Multiple common mode traps in all receive coil cables. **6)** Minimum of 5 mm spacing between coil conductors and patient contact.

Additionally, the coil was designed and manufactured under an ISO 13485 certified quality management system. As part of this quality system, Nova Medical has conducted a failure means and effects analysis (FEMA) of this product, and we feel that it is a nonsignificant risk under foreseeable normal conditions when used on the 3T GE X750 MRI scanners at MCW.

7.3. MRI Safety Screening

MCW-specific magnetic resonance (MR) safety screening procedures will be followed. All participants will be screened for medical devices, implants, and metal prior to undergoing MRI, first at the screening and baseline visits (Visits -1 and 1) and again prior to Visits 10, 12, and 22. If it is necessary to review medical records to confirm contraindication, a review of medical records (e.g., previous surgeries) will take place prior to the scheduled visit. During the screening process, participants will also be questioned about their ability to temporarily remove transdermal patches (such as birth control or nicotine patches). Women of child-bearing potential will be asked to confirm that they are not pregnant when signing the ICF. If a woman has concerns or is uncertain of her pregnancy status, she will be excluded, as the risks of an MRI scan to pregnant women are currently unknown. The risks related to an MRI are minimal for a properly administered visit. The MR technicians are trained and prepared to deal with any problems that may arise.

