5.4.2. Demographics, Medical History, and MRI Safety Screening

Demographic information, basic medical history, and MRI safety screening begin at the screening visit and are completed at baseline prior to any study participation by the subject. Data are collected from participants including demographic information (age, gender, race, ethnicity), medical and surgical history, hospitalization history, medications and supplements, and family history of illness. We will also ask questions pertaining to fluency in languages, education, history of dyslexia or other developmental learning disabilities, and work history.

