5.4.5. Neuroimaging Assessments

The acquisition strategy for IvPPA participants is to collect datasets that include resting-state functional MRI (rs-fMRI), diffusion MRI (dMRI), and resting state magnetoencephalography (rsMEG).

MRI Acquisition Protocols

All IvPPA patients will undergo four 60-minute 3T MRI scanning sessions (total 4 hrs), including high-resolution T1 and T2 structural MRI, dMRI, and rs-fMRI as summarized below. In the case of left handed participants (approximately 80% are left hemispheric dominant), they will undergo a quick fMRI test (~ 6 min) to confirm their left hemispheric dominance (Binder et al. 1995).

3T MRI Hardware: Scanning will be done on GE MR 750 3T clinical scanners (50 mT/m & 200 T/m/s gradients) with a Nova 32-channel neuroimaging phased array receive head coil and whole-body rf transmission.

3T MRI Pulse Sequences: fMRI and diffusion MRI acquisitions will use prototype GE pulse sequences from the "ProtoPak2" software package, made available to us by a research agreement with GE. These state-of-the-art sequences provide multi-band acquisition of fMRI and dMRI data, greatly accelerating the acquisitions and allowing reductions in voxel size and repetition time to match those of the HCP protocol.

Resting-State fMRI (rs-fMRI) Protocol. The rs-fMRI parameters will be identical to the HCP Lifespan protocol, including an eyes-open fixation task, 30 minutes of rs-fMRI data divided into six 5-minute runs, and a 50:50 alternation of phase encoding direction.

Structural MRI Protocol. T1-weighted structural images will be acquired using the GE "BRAVO" pulse sequence and "Cube" with "ARC" for T2-weighted images, which is a 3D fast spin echo sequence using GE's autocalibrated parallel imaging technology. These vendor-supplied sequences provide comparable image quality to those of the HCP at the same 0.8 mm isotropic voxel size.

Prior to fMRI scans, subjects will undergo MRI safety screening and, as detailed in sections 7.3. and 7.4., respectively.

MEG Acquisition Protocol

MEG offers relatively good spatial localization of neural activity sources together with millisecond temporal resolution not possible with hemodynamic imaging methods. All IvPPA patients will undergo resting state MEG recordings.

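### Section 7.3 lists MRI safety re-screening before Visit 22, which has no MRI, instead of Visit 21, which has the last one, and times its only stated pregnancy confirmation at consent

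*Protocol*

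**What the plan says.** Protocol section 7.3 opens by adopting local rules: "MCW-specific magnetic resonance (MR) safety screening procedures will be followed". It then states: "All participants will be screened for medical devices, implants, and metal prior to undergoing MRI". The timing given is "first at the screening and baseline visits (Visits -1 and 1) and again prior to Visits 10, 12, and 22".

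On pregnancy, the same section says: "Women of child-bearing potential will be asked to confirm that they are not pregnant when signing the ICF". A woman who is unsure of her status is to be excluded, "as the risks of an MRI scan to pregnant women are currently unknown". Section 5.4.1 places the signing of consent at Visit -1.

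Three other places bear on the point:

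- Section 5.4.5 (Neuroimaging Assessments) says that participants "will undergo four 60-minute 3T MRI scanning sessions". It adds: "Prior to fMRI scans, subjects will undergo MRI safety screening", and refers to 7.3 for the detail.
- Section 5.4.2 says that demographics, history and "MRI safety screening begin at the screening visit and are completed at baseline prior to any study participation by the subject".
- Section 5.1 places the scans at Visits 1, 10, 12 and 21. It describes Visit 22 as the language battery with the trained tasks.

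**The concern.** There are two separate matters in one short section.

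The first is the visit list. Staff use such a list to build the visit checklist. As written, it calls for a screen before a visit that has no scanner session and does not name the visit with the last one. The screen for implants and metal concerns every participant, not only women who could be pregnant.

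The second is the timing of the pregnancy question. The protocol's reason for excluding a woman who is unsure is a property of the scan, so it holds as much for the fourth scan as for the first. An answer given at consent says nothing about status months later. The repeat screening in 7.3 is described in terms of devices, implants, metal and removable patches, and pregnancy is not among the items repeated. A reader cannot tell from the protocol whether the question is asked again.

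**Working it through.** **Step 1. Which visits have an MRI?** Section 5.1 names Visits 1, 10, 12 and 21. Three checks agree with it:

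- Section 5.4.5 gives four sessions.
- The fMRI row of Table 1 has four marks. Footnotes g, h and i tie them to before Period 1, after each period and before Period 2, so this reading does not depend on column alignment.
- Section 5.2 pays \$30 for Visits 1, 10, 12 and 21, \$7 for Visits 2-9 and 13-20, and \$17 for Visits 11 and 22. The stated total is reproduced: 4 × 30 + 16 × 7 + 2 × 17 = 120 + 112 + 34 = \$266. Visit 22 is paid as an assessment visit, like Visit 11.

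**Step 2. Compare with the list in 7.3.**

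| Visit | MRI (5.1) | Listed for screening in 7.3 |
|---|---|---|
| -1 | no | yes |
| 1 | yes | yes |
| 10 | yes | yes |
| 12 | yes | yes |
| 21 | yes | **no** |
| 22 | no | **yes** |

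The only mismatch among the re-screening visits is 22 in place of 21. Read literally, the last listed screen before the final scan is the one for Visit 12. The Visit 12 scan may be up to 3 months before Period 2, and the Visit 21 scan up to 1 month after it. The two scans are therefore 2 weeks apart with no windows, and up to 13 + 2 + 4.35 = 19.35 weeks apart with both windows used.

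**Step 3. Time from consent to each scan.** Week 0 is the first session of Period 1. Inputs:

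- two treatment periods of 2 weeks and a washout of 16 weeks (Protocol Summary), with the washout held fixed;
- a lead-in of up to 3 months for Visit -1 and Visit 1 procedures (5.1);
- a post-treatment scan window of up to 1 month (5.1; Table 1 footnote h).

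Assumed conversions: 3 months = 13 weeks, 1 month = 4.35 weeks.

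| Scan | No windows (weeks) | Lead-in and scan window fully used (weeks) |
|---|---|---|
| Visit 1 | 0 | 13 |
| Visit 10 | 2 | 13 + 2 + 4.35 = 19.35 |
| Visit 12 | 2 + 16 = 18 | 13 + 18 = 31 |
| Visit 21 | 2 + 16 + 2 = 20 | 13 + 20 + 4.35 = 37.35 |

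Because the Visit 12 scan may be brought forward by 3 months, it can also fall as early as week 18 - 13 = 5. If a treatment period is counted as the 11 days from first to tenth session, the 20 weeks becomes 1.57 + 16 + 1.57 = 19.1. The conclusion does not change.

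**Step 4. Count the stated pregnancy confirmations.** There is one, at consent, against four scans. No other section states a question or test, and Table 1 has no row for it.

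**The case against.** The strongest reply is that the working rule is sound and only a number is wrong. Both 5.4.5 and 7.3 require screening before MRI in general terms, so the Visit 21 scan is covered whatever the list says. That stands. A reader might infer from the list that the last scan is done without a safety screen, but the documents do not support that inference.

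The second reply is that local MR procedures may well ask about pregnancy before every scan. Their content is not in the documents, and the consent form is not there either. The exclusion of a woman who is unsure is not expressly limited to the time of consent, and contraindications to MRI are an exclusion criterion in 4.2. This also stands, as far as it goes. One may not conclude that later scans are done without a pregnancy check. One may conclude that the protocol does not say whether there is one, and that the section to which 5.4.5 refers does not supply it.

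Third, a longer interval could be computed by adding the +1 month treatment-visit windows of Table 1. I do not use it. Those windows at Visits 10 and 21 may be the same month as the scan window, so adding them risks counting it twice. Section 5.4.5 on treatment dosing also fixes treatment at two consecutive weeks.

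Fourth, Table 1 is weak evidence as extracted. A Language Battery mark sits under Visits 2-9 although footnote f assigns it to Visit 10. I therefore draw nothing from where the marks in the MRI safety screening row fall, beyond a reason to check that row against 7.3.

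Last, all 20 participants are 45 or older, so few women, or none, may be concerned. That is right, and it limits the weight of the pregnancy part. The protocol nevertheless provides for such women, and 6.8 lists childbearing potential among the data items.

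**Conclusion.** Both parts hold in limited form. The re-screening list in 7.3 is wrong: it names Visit 22, which has no MRI, and omits Visit 21, which has the last. The only pregnancy confirmation given a time is at consent, about 20 to 37 weeks before the last MRI, although its stated reason applies to every scan. These are faults in the protocol text. They are not evidence that any scan was done without screening.

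The week figures rest on the month conversions above and on a washout of exactly 16 weeks. The number of women of child-bearing potential is not given and may be zero. The practical safety gain is small, and endpoints and analysis are not affected. The SAP is written in the past tense, so participants may no longer be exposed. In that case the correction matters mainly if this text is reused for a later trial. I rate it a minor correction worth making.

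**What to change.** 1. In 7.3, replace Visit 22 by Visit 21 in the re-screening list.
2. In 7.3, add one sentence requiring women of child-bearing potential to reconfirm at the safety screening before each of the four MRIs that they are not pregnant. If the MCW procedures already do this, a sentence saying so is enough.
3. Make the MRI safety screening row of Table 1 consistent with the corrected 7.3.

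The cost is one visit number, one sentence and a check of one table row. In use, it adds one short question per scan, so at most four per woman concerned. No new data item is needed to know whom to ask, since childbearing potential is already among the items listed in 6.8.
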